4.8.3 Deaths

Details of any deaths will be presented in the form of an individual patient listing.

4.8.4 Laboratory Data

4.8.4.1 Safety Laboratory Parameters

All laboratory data will be converted to SI units. The International Standard for the Handling and Reporting of Laboratory Data COG 3007 will be used to implement reference ranges and marked abnormalities for laboratory data where possible. Additionally, serum creatinine, hemoglobin, albumin and hematocrit will be presented in conventional units.

Summary statistics for the absolute and change from baseline values will be produced by visit for laboratory parameters.

Marked abnormalities will be summarized for laboratory parameters. Summaries by National Cancer Institute Common Terminology Criteria for Adverse Events (NCI CTCAE) grade will also be produced for certain lab assessments, including shift tables from baseline to highest grade post-baseline.

Shift tables from baseline to highest NCI CTCAE grade post-baseline will be produced for liver function laboratory tests.

4.8.4.2 Immunoglobulins

The absolute values and change from baseline will be summarized by treatment group and visit for total Ig, IgA, IgG, and IgM.

The proportion of patients with a value of total Ig, IgA, IgG, and IgM which is less than the lower of limit of normal per visit will be produced.

A plot of the mean value over time will be produced for total Ig, IgA, IgG, and IgM. The plots will display error bars (mean±standard deviation) around the mean.

4.8.5 Vital Signs

Vital signs are measured at each scheduled visit in accordance with the schedule of assessments (see protocol). At infusion visits, vital signs should be taken pre-infusion, then every 15 minutes for 1 hour, then every 30 minutes until the end of the infusion, and within 30 minutes post-infusion. Additional readings may be obtained at the discretion of the investigator in the event of an infusion-related reaction.

Summary tables for the absolute value and change from baseline in vital sign assessments will be presented by visit. Vital sign assessments include respiratory rate, pulse rate, temperature, systolic and diastolic blood pressure. Body mass index will be calculated for these time points that body weight is measured.

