#### **Obinutuzumab Dose and Schedule**

Obinutuzumab will be administered by IV infusion as an absolute (flat) dose of 1000 mg for four infusions on Days 1, 15, 168, and 182. Placebo infusion will be infused in the same volume and on the same scheduled days in the control arm.

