#### **6.5.4 Vital Signs**

The change from pretreatment (measured just before initiation of the infusion) in vital signs recorded during infusion and post-infusion will be summarized. Vital signs that are obtained during screening and the follow-up period will also be summarized.

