2.2.4 Safety Outcome Measures

The safety outcome measures are as follows:

- Incidence, type, and severity of adverse events (AEs) and adverse events of special interest (AESI), including infusion reactions, infections, thrombocytopenia, and neutropenia
- Proportion of patients with abnormal vital signs
- Proportion of patients with abnormal laboratory values

Safety will be monitored through regular physical examinations, vital signs, hematologic and chemistry laboratory tests, urinalyses, and incidence and severity of AEs.

In addition, the following will be examined:

- Circulating B cells, T cells, neutrophils, and other cell populations
- Plasma immunoglobulins (total immunoglobulin [Ig], immunoglobulin G [IgG], immunoglobulin M [IgM], and immunoglobulin A [IgA])
- Pregnancy
- Antibody titers for mumps, rubella, varicella, tetanus, influenza, and *Streptococcus pneumoniae*

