4.9.2 Definitions

Baseline

Baseline is defined as the last non-missing value prior to receipt of study treatment. Typically, baseline will be the pre-dose Day 1 assessment, but may include screening results if the pre-dose Day 1 result is not available or missing. If the Day 1 or screening result is missing, then no imputation will be made and the baseline result will be set to missing.

Study Day

For each patient, the first day of study treatment will be designated study Day 1. Each subsequent assessment will be assigned a study day calculated as:

$$\text{date of assessment} - \text{date of first dose} + 1$$

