4.9.3 Multiple Values

For summaries displayed by visit, multiple values for a given assessment within a time window will be handled as follows:

Efficacy

The nearest non-missing assessment to the nominal timepoint will be assigned to the visit. If two or more values are equidistant from the nominal timepoint, then the latest assessment will be selected.

Safety

The assessment with the worst result will be assigned to the visit.

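### The SAP's vital-sign tables cannot give the within-infusion change that protocol 6.5.4 plans: they use the Day 1 baseline and keep only the worst reading per visit

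*SAP*

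**What the plan says.** Protocol 6.5.4 sets the infusion analysis: "The change from pretreatment (measured just before initiation of the infusion) in vital signs recorded during infusion and post-infusion will be summarized". It adds summaries of screening and follow-up vital signs.

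SAP 4.8.5 repeats the dense measurement schedule for infusion visits ("vital signs should be taken pre-infusion, then every 15 minutes for 1 hour", then every 30 minutes to the end, and once more within 30 minutes afterwards). The only analysis it then plans is: "Summary tables for the absolute value and change from baseline in vital sign assessments will be presented by visit".

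Two general rules fix what that means:

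- SAP 4.9.2: "Baseline is defined as the last non-missing value prior to receipt of study treatment". It continues: "Typically, baseline will be the pre-dose Day 1 assessment". There is no exception for vital signs and no reference specific to an infusion.
- SAP 4.9.3, for safety data with several values in one visit window: "The assessment with the worst result will be assigned to the visit".

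SAP 2.2.4 lists a third measure among the safety outcomes: "Proportion of patients with abnormal vital signs". Section 4.8.5 has no table for it and gives no thresholds. For laboratory data, by contrast, 4.8.4.1 plans a summary of marked abnormalities, and 4.8.4.2 plans the proportion of patients with immunoglobulins below the lower limit of normal.

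**The concern.** The readings around each infusion exist to show what the infusion does to blood pressure, pulse, respiratory rate and temperature. The reading just before the infusion is the natural reference, and the protocol names it. The SAP replaces it with a value that, at the third and fourth infusions, is more than five months old. It then keeps one reading per visit, so the pre-, during- and post-infusion values are no longer distinguishable.

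Infusion-related reactions are adverse events of special interest in protocol 5.2.3, and the schedule of assessments gives hypotension and fever as examples. Effects on vital signs are also part of the safety objective in protocol 2.2. At stake is whether the final report contains the objective measurement of infusion effects that the protocol planned. Nothing in the SAP says that this summary was dropped or moved.

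**Working it through.** Neither document states a figure for this analysis, so there is none to reproduce. The check compares definitions and elapsed time.

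**Inputs.** Infusion days: "four infusions on Days 1, 15, 168, and 182" (protocol 4.3.2.1). Protocol reference: the reading just before the infusion. SAP reference: usually pre-dose Day 1. Visit windows: midpoints between scheduled visits (SAP 4.5). Uninterrupted infusion times: 255 minutes for the first infusion and 195 for later ones (protocol Appendix 7).

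**Age of the reference value.** SAP gap = infusion day minus 1. The protocol reference is read on the same day.

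| Infusion day | Protocol gap (days) | SAP gap (days) | SAP gap in other units |
|---|---|---|---|
| 1 | 0 | 0 | none |
| 15 | 0 | 14 | 14/7 = 2.0 weeks |
| 168 | 0 | 167 | 167/30.44 = 5.5 months |
| 182 | 0 | 181 | 181/30.44 = 5.9 months |

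**What each measure estimates.** Take one during-infusion reading. Let e be the acute infusion effect and d the shift in the patient's pre-infusion level since Day 1. The protocol change estimates e; the SAP change estimates e + d. They agree when d = 0, as on Day 1. By Day 168 the prednisone taper to 7.5 mg/day by Week 12 (protocol 4.3.2.3) lies within the interval, so d need not be zero. Between arms, the SAP difference is (e_O − e_P) + (d_O − d_P). The second bracket vanishes if drift is the same in both arms and remains if it differs.

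**Readings lost to the worst-value rule.** The schedule implies, for an uninterrupted infusion:

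- First infusion: 1 before, 4 in the first hour, 6 at 90 to 240 minutes, 1 after = 12.
- Later infusions: 1 before, 4 in the first hour, 4 at 90 to 180 minutes, 1 after = 10.

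Each set becomes one visit value, so no pre-to-post difference can be formed from the tables. If the readings were independent and the infusion had no effect, the worst of 10 would lie on average 1.54 within-visit SDs from the mean, and the worst of 12 would lie 1.63 SDs away. Correlation between readings would shrink this. The SAP also does not say whether the worst blood pressure, pulse or temperature is the highest or the lowest.

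**Which day the value comes from.** With vital signs at every scheduled visit, the midpoints around Days 168 and 182 are (84 + 168)/2 = 126, (168 + 182)/2 = 175 and (182 + 252)/2 = 217. SAP Table 1 places the midpoint day in the earlier window. The Day 168 window is then Days 127 to 175, and the Day 182 window is Days 176 to 217. If an unscheduled reading falls in the window, the worst value need not come from the infusion day.

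**The case against.** **Scope.** SAP version 2 covers the final report only, and the Week 52 and Week 104 reports are already issued. The last infusion is on Day 182, so the scheduled infusion-day readings predate both. The infusion summary may already exist, and a reader might wrongly infer that the trial never planned or reported it. The documents do not show that, because the earlier SAP and reports are not among them. They do not show the opposite either. SAP 4.7 says outright that PK parameters were determined in previous reports; 4.8.5 says nothing similar, and 4.8 makes all safety outputs cumulative to the final lock.

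**Infusion reactions are covered elsewhere.** They are recorded as adverse events with a dedicated form (protocol 5.3.5.1), clinically significant vital-sign changes must be reported as adverse events (5.3.5.6), and SAP 4.8.2 reports infusion-related reactions and serious ones. This stands: it would be wrong to infer that infusion hypotension or fever goes unreported. However, those records depend on the investigator's judgement, and the protocol plans the measured change as well.

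**Drift.** A reader might infer that months of drift affect every infusion, or that the arm comparison is confounded. Neither follows. Day 1 has no reference mismatch, Day 15 is two weeks later, and common drift cancels between randomised arms. Protocol 5.1.1 reports that reactions in CLL and NHL studies occurred mainly with the first 1000 mg. Blood-pressure titration is also partly complete before Day 1, because protocol 4.4.1.1 asks for an ACE inhibitor or ARB for at least 10 days before randomisation.

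**Wording of 6.5.4.** It refers to the infusion, not to each infusion, and does not mention lowest or highest change. The per-infusion reading is the natural one, but extremes are not a protocol commitment.

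**Table layout.** A programmer might show each scheduled time within a visit separately. SAP 4.9.3 does not provide for that, and the baseline would still be the one in 4.9.2.

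**Conclusion.** The mismatch stands on the text. Under SAP version 2, the within-infusion change in protocol 6.5.4 cannot be obtained from the planned tables. At Days 15, 168 and 182, the reported change within each arm mixes the acute effect with 14, 167 and 181 days of background change. On Day 1 the reference agrees, but the worst-value rule still leaves one reading per visit. Separately, the abnormal-value proportion named in SAP 2.2.4 has no table.

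This rests on reading 6.5.4 as applying to each infusion and on applying SAP 4.9.2 and 4.9.3 as written. It concerns descriptive safety tables in the final report. No endpoint, alpha, power or sample size changes.

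A reader might be tempted to price the choice of reference as a multiple of the sample size. The documents do not support a figure. Assume, for illustration, an SD of 15 mmHg for systolic change between visits and 8 to 10 mmHg within a visit. Treating the two changes as independent gives variance ratios of (225 + 64)/64 = 4.5 and (225 + 100)/100 = 3.25. Allowing for the pre-infusion reading they share, with independent reading errors, gives 225/64 = 3.5 and 225/100 = 2.25. The SDs are assumptions, the formula ignores the worst-value rule, and the plan has no vital-sign test or power target to which a ratio could apply.

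**What to change.** In SAP 4.8.5:

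1. For Days 1, 15, 168 and 182, summarise by arm the change from that day's pre-infusion reading to the scheduled during- and post-infusion readings.
2. Exempt these readings from the worst-value rule in 4.9.3. Where that rule still applies to vital signs, state which direction counts as worst.
3. Keep change from the Day 1 baseline for pre-infusion values and non-infusion visits.
4. Add the by-arm proportion of patients with abnormal vital signs named in 2.2.4, with its thresholds.

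If an earlier study report already contains the infusion analysis, say so in 4.8.5, as 4.7 does for PK; item 1 then needs no repeat. The cost is SAP wording and an extra descriptive table from data already collected, with the abnormal-value summary alongside.

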4.9 DATA HANDLING METHODS

4.9.1 Presentation of Data

Data displays include listings, tables, and plots. All data displays will be presented by treatment group.

Data presented in summary tables will be displayed using summary statistics. Continuous data will include number of patients, mean, standard deviation, median, minimum, and maximum. Categorical data will include the number and percentage of patients.

4.9.2 Definitions

Baseline

Baseline is defined as the last non-missing value prior to receipt of study treatment. Typically, baseline will be the pre-dose Day 1 assessment, but may include screening results if the pre-dose Day 1 result is not available or missing. If the Day 1 or screening result is missing, then no imputation will be made and the baseline result will be set to missing.

Study Day

For each patient, the first day of study treatment will be designated study Day 1. Each subsequent assessment will be assigned a study day calculated as:

$$\text{date of assessment} - \text{date of first dose} + 1$$

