4.6.1.2 Serum Creatinine

Only creatinine data obtained from the central laboratory will be used for efficacy analysis.

Missing Data: If Day 1 serum creatinine data is missing, then the screening value will be used. Missing post-baseline serum creatinine will be imputed using the value from the previous visit. If the previous visit is still missing, no imputation will be made, unless otherwise specified.

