4.6.1.3 Inactive Urinary Sediment

Urine sediment data from the local laboratory will be prioritized in the efficacy analysis given the time-sensitive nature of this analysis and the delay between local specimen collection and central laboratory analysis. The central laboratory data will be used when local laboratory data are missing using the strategy highlighted below.

Missing Data

Missing urine sediment data at Day 1 will be imputed in the following order:

- Urine sediment data at Day 1 (central lab)
- Urine sediment data from screening (local lab)
- Urine sediment data from screening (central lab)

Missing post-baseline RBC counts will be imputed in the following order:

- RBC counts at the same visit (central lab)
- RBC counts from the previous visit (local lab)
- RBC counts from the previous visit (central lab)

If the value is still missing, then no imputation will be made.

Missing post-baseline RBC casts will be imputed in the following order:

- RBC casts at the same visit (central lab)
- RBC casts from the previous visit (local lab)
- RBC casts from the previous visit (central lab)

If the central laboratory value from previous visit is still missing, then “casts absent” will be imputed.

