4.6.1.4 Urinary Protein to Creatinine Ratio

Only Urinary Protein to Creatinine Ratio (UPCR) (mg/mg) data obtained from the central laboratory will be used for efficacy analysis with the exception of the first 4 patients enrolled into the study. Through a laboratory error, baseline UPCR was not calculated for these subjects. In this case, local values for UPCR will be used, if available.

Missing Data

Missing 24-hour UPCR at Day 1 will be imputed in the following order:

- 24-hour UPCR from the screening visit (central laboratory)
- Spot UPCR from the Day 1 visit (central laboratory)
- Spot UPCR from the screening visit (central laboratory)

Missing post-baseline 24-hour UPCR will be imputed in the following order:

- Spot UPCR from the same visit (central laboratory)
- 24-hour UPCR from the previous visit (central laboratory)
- Spot UPCR from the previous visit (central laboratory)

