4.6.3.3 Physician's Global Assessment (PGA)

Absolute value at each visit and change from baseline in PGA over 52 weeks will be presented in each arm using summary statistics to show the trends over time.

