4.7 PHARMACOKINETIC AND PHARMACODYNAMIC ANALYSES

Pharmacokinetic (PK) parameters have been determined for all patients with serum concentration data in the previous CSRs. A list of PK and ADA values will be presented in the final CSR.

The primary pharmacodynamic (PD) marker will be CD19⁺ B-cell counts. Exploratory PD markers from blood samples may be summarized graphically and descriptively over time by treatment arm.

In addition, the percent change from baseline for each marker will be computed at each sampling timepoint using the Day 1 pre-dose value as the baseline point.

Exploratory analyses may be performed to assess the possible relationship between obinutuzumab dosing, PD markers, PK measures, and clinical response.

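### SAP 4.9.2 sets baseline to missing when either the Day 1 or the screening result is missing, which contradicts its own definition for variables with no baseline rule of their own

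*SAP*

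**What the plan says.** The baseline definition in SAP 4.9.2 has three sentences.

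1. The general rule: "Baseline is defined as the last non-missing value prior to receipt of study treatment".
2. The back-up: the value is usually Day 1 pre-dose, but baseline "may include screening results if the pre-dose Day 1 result is not available or missing".
3. The closing rule: "If the Day 1 or screening result is missing, then no imputation will be made and the baseline result will be set to missing".

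Other sections set baseline rules for particular variables.

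- **Serum creatinine (SAP 4.6.1.2):** "If Day 1 serum creatinine data is missing, then the screening value will be used".
- **Urine sediment (SAP 4.6.1.3):** "Missing urine sediment data at Day 1 will be imputed in the following order". The order is Day 1 central laboratory, then screening local, then screening central.
- **Urine protein to creatinine ratio (SAP 4.6.1.4):** "Missing 24-hour UPCR at Day 1 will be imputed in the following order". The order is screening 24-hour, then Day 1 spot, then screening spot.
- **Pharmacodynamic markers, including CD19+ (SAP 4.7):** percent change is computed "using the Day 1 pre-dose value as the baseline point".

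SAP 4.6.2.2 plans change from baseline for anti-dsDNA, C3 and C4. For missing data it offers only last observation carried forward and says nothing on baseline.

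**The concern.** The third sentence joins the two results with *or*, so on its plain wording one missing result is enough to remove baseline. That contradicts the two sentences before it and runs against the screening fallbacks that the SAP writes out for creatinine, sediment and protein to creatinine ratio.

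This is the SAP's general definition, so it governs every change-from-baseline analysis that has no rule of its own. A programmer who follows it literally would drop patients who have a usable pre-treatment value. Two programmers could also reach different denominators from the same text. The most consequential place is the fixed testing sequence in SAP 4.6, where a step with p not below 0.20 bars a claim of significance for all later endpoints.

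**Working it through.** No figure in the plan depends on this sentence, so the check is logical.

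**Step 1. Compare the sentences over all combinations of the two results.**

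| Day 1 | Screening | Sentences 1 and 2 | Sentence 3 with *or* | Sentence 3 with *both* |
|---|---|---|---|---|
| present | present | Day 1 | Day 1 | Day 1 |
| present | missing | Day 1 | missing (conflict) | Day 1 |
| missing | present | screening | missing (conflict) | screening |
| missing | missing | none | missing | missing |

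The literal text conflicts in 2 of 4 combinations. With *both*, it agrees in 4 of 4.

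**Step 2. Find which variables depend on 4.9.2.** Inputs are the schedule in SAP Appendix 2 and the analysis sections.

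| Variable | Scheduled at screening / Day 1 | Own baseline rule | Exposed? |
|---|---|---|---|
| Creatinine, sediment, protein to creatinine ratio | yes / yes | SAP 4.6.1.2 to 4.6.1.4 | no |
| CD19+ and other PD markers from flow cytometry | no / yes | SAP 4.7 | no |
| Anti-dsDNA, C3, C4 | yes / yes | none in 4.6.2.2 | yes |
| Safety laboratory tests (other than those in row 1), vital signs | yes / yes | none in 4.8.4 or 4.8.5 | yes |
| Subject's and Physician's Global Assessments | no / yes | none in 4.6.3.3 or 4.6.3.4 | possibly |

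**Step 3. The global assessments.** SAP 4.6.3.3 plans "Absolute value at each visit and change from baseline in PGA over 52 weeks", and 4.6.3.4 plans the same for the patient scale. The schedules in Protocol Appendix 1 and SAP Appendix 2 mark both scales on Day 1 and not at screening. Protocol 3.4.5 and 3.4.6 say both are captured in screening. If the schedule is right and a result never scheduled counts as missing, the literal rule leaves no patient with a baseline. If the protocol text is right, only patients lacking one value are affected.

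**Step 4. Place in the testing sequence.** Anti-dsDNA, C3 and C4 are steps 5, 6 and 7 of 12. A failure at step 5 closes 12 − 5 = 7 later endpoints, and a failure at step 7 closes 12 − 7 = 5.

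**Step 5. Number of patients.** If a fraction *q* lacks exactly one of the two results for a variable, the literal rule removes *q* × 120 patients from its change from baseline at the planned sample size. The documents give no value for *q*, so this stays a formula.

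**Step 6. Design figures.** With 60 per arm, response rates of 30% and 50% and two-sided alpha 0.2, power recomputes to 0.835, in line with the stated 83%. Baseline handling does not enter that calculation.

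**The case against.** The best defence is that the sentence has a consistent reading: if the baseline result (Day 1 or, failing that, screening) is missing, nothing further is imputed. Sentences 1 and 2 point that way. So do the three component rules and Table 1 in SAP 4.5, which assigns any urinalysis up to Day 1 to baseline. This is probably what the authors meant. It is not what the words most plainly say, and a general definition should not have to be rescued from its context.

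A second defence is that carrying the last observation forward (SAP 4.6.2.2) already covers anti-dsDNA, C3 and C4. That section does not say the method reaches back to baseline, and 4.9.2 rules out imputation there. Even if it did, it could only supply screening for a missing Day 1 value. It would not restore a Day 1 value voided because screening is absent.

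A third is that few patients should lack a screening result, since Protocol 4.5.1 requires screening evaluations to be completed and reviewed before randomization. That is fair and limits the likely size.

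Four stronger inferences are tempting, and the documents do not support them.

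- **Patients become non-responders for complete renal response.** SAP 4.6.1.1 applies that default only after the component imputation rules, and those rules use screening when Day 1 is absent. None voids a valid Day 1 value. SAP 4.6.2.1, 4.6.2.4 and 4.10 send partial response, the modified responses and efficacy missing data generally to the same place. A cost in response-rate points (one patient in 60 is 1/60 = 1.7 points) therefore has no basis.
- **CD19+ loses its baseline in every patient because flow cytometry is not done at screening.** SAP 4.7 and Protocol 6.6 fix the Day 1 pre-dose value as baseline.
- **The Glucocorticoid Toxicity Change Index loses its baseline.** It is scheduled on Day 1 only, but SAP 2.2.3 does not list it for the final report.
- **The global assessments certainly lose baseline in all patients.** That needs the schedule to be right over the protocol text, and an unscheduled result to count as missing.

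**Conclusion.** The sentence is wrong as written and should be corrected. It contradicts the definition it closes in 2 of 4 combinations. It governs change in anti-dsDNA, C3 and C4, safety laboratory and vital-sign changes, and possibly the two global assessments. The primary endpoint, partial response, CD19+, power and alpha are untouched.

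The practical size is unknown and probably small. It depends on two things the documents do not show: how many patients have only one of the two results, and whether the programs follow the literal text or the evident intent. The link to the testing sequence also assumes that steps 5 to 7 are tested as SAP 4.6 lists them. This is a low-cost clarification of an operative rule and does not threaten the main result.

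**What to change.** Replace the last sentence of the baseline definition in SAP 4.9.2 with: *If both the Day 1 pre-dose result and the screening result are missing, baseline is left missing and nothing is imputed.* Add one sentence: *Sections 4.6.1.2 to 4.6.1.4 and 4.7 take precedence for the variables they cover.*

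Also reconcile the screening collection of the two global assessments between Protocol 3.4.5 and 3.4.6 and the schedules, so that it is clear whether a screening back-up exists for them. Before the final report is programmed, confirm that the derivation code uses the *both* reading.

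The cost is two sentences in the SAP and a code check. No design figure changes.
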